STATISTICAL ANALYSES PLAN

Acute exercise and coronary heart disease risk markers in healthy male smokers and non-smokers

Version 1

Investigators

[name]

[name]

Address

School of Sport, Exercise and Health Sciences

Loughborough University

Leicestershire

[name]

United Kingdom

Correspondence

[name]: [name], [contact]

Statistical analyses plan

The data collected will be analysed using the software package SPSS (SPSS version 23, SPSS Inc., Chicago, IL). The distribution of the outcome variables will be explored using histograms. Normally distributed data will be presented as mean (SD). Variables deemed to show a positively skewed distribution will be natural log transformed prior to analysis, and negatively skewed variables will be reflected before natural log transformation. These data will be presented as geometric mean (95% confidence interval) and analysis will be based on ratios of geometric means and 95% confidence intervals for ratios.

Physical characteristics and exercise responses will be compared between smokers and non-smokers using linear mixed models with smoking status included as a fixed factor. The homeostasis model assessment of insulin resistance (HOMA-IR) will be calculated as follows (Matthews *et al.* (1985) *Diabetologia* 28: 412–419):

$$\text{HOMA-IR} = \frac{\text{Fasting glucose} \times \text{Fasting insulin}}{22.5}$$

Total area under the plasma concentration versus time curve (AUC) will be calculated for plasma constituents and blood pressure using the trapezoidal method. Linear mixed models will be employed to examine differences in dietary intake, habitual physical activity and sedentary time, HOMA-IR and fasting and AUC plasma constituents and blood pressure with condition (exercise versus control) and group (smokers versus non-smokers) included as fixed factors. Models for habitual physical activity and sedentary time will include wear time as a covariate. Differences in postprandial plasma constituents and blood pressure over time will be examined using linear mixed models repeated for condition, group and time.

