Absolute standardised effect sizes will be calculated by dividing the difference between the mean values (exercise versus control or smokers versus non-smokers) with the pooled standard deviation. In the absence of a clinical anchor, an effect size of 0.2 will be considered the minimum important difference, 0.5 moderate and 0.8 large (Cohen 1988 *Statistical power analysis for the behavioural sciences*, 2nd edn., Lawrence Erlbaum Associates, Hillsdale (NJ)). Statistical significance will be accepted as $P < 0.05$.

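### Does listing smoking group among the repeated factors make the time-course analysis wrong?

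*SAP*

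**What the plan says.** The time-course model is specified in one sentence, at the end of the third paragraph of the SAP's only section (Statistical analyses plan). Postprandial outcomes will be "examined using linear mixed models repeated for condition, group and time". The sentence names no subject variable and no covariance structure.

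Three other places show what group is:

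- The title, "Acute exercise and coronary heart disease risk markers in healthy male smokers and non-smokers", describes two kinds of men.
- The second paragraph has physical characteristics and exercise responses "compared between smokers and non-smokers using linear mixed models with smoking status included as a fixed factor".
- Earlier in the third paragraph, the fasting and AUC models are fitted "with condition (exercise versus control) and group (smokers versus non-smokers) included as fixed factors".

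The fourth paragraph makes the smoking comparison one of the two contrasts that receive standardised effect sizes ("exercise versus control or smokers versus non-smokers") and sets significance at the 5% level.

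**The concern.** A repeated factor is one whose levels are observed more than once in the same subject. Time is such a factor. Condition is too, if the word repeated is taken to mean that each man does both exercise and control. Smoking status is not: nothing in the SAP has a man change status or matches a smoker to a non-smoker. Read strictly, the sentence misclassifies one of its three factors.

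The choice of error term is what could be at stake. A difference between smokers and non-smokers must be judged against the variation between men. If software were led to treat group as varying within a subject, the smoking contrast would be tested against within-subject error. Its standard error would be too small, and false smoking differences would become more likely. That contrast is in the trial's title, so the wording deserves a check.

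**Working it through.** **Inputs.** From the SAP: two conditions, two groups, group as a fixed factor elsewhere, 5% significance. Assumed, because the SAP does not give them: T = 5, 7 or 9 time points, 12 men per group, compound symmetry within a man with correlation ρ = 0.2 to 0.8, no true effects. The SAP states no figure on this point to reproduce.

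**Step 1: what one man contributes.** Crossing condition, group and time gives 4T cells. A man fills only the 2T cells of his own group; at T = 7 that is 14 of 28. Listing group adds no repeated observation within a man.

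**Step 2: group listed as repeated, each man with his own identifier.** Take T = 7.

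- An unstructured matrix over all cells has 28 × 29 / 2 = 406 parameters.
- Of these, 14 × 14 = 196 pair a smoker cell with a non-smoker cell. No man has both, so they enter nobody's likelihood.
- The remaining 406 − 196 = 210 are two blocks of 14 × 15 / 2 = 105, one per group. With only condition and time as repeated factors there would be one block of 105.

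So listing group at most gives smokers and non-smokers separate covariance blocks. Under compound symmetry each man's block is the same as without it. Simulated type I error for the group main effect:

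| Model, unique identifier | Type I error |
|---|---|
| Common compound symmetry (20,000 replicates per setting) | 4.7% to 5.2% |
| Separate variances by group, Welch test on man means (40,000 replicates) | 4.7% to 5.0% |

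A fully unstructured fit over all 28 cells might fail to converge, but that failure would be visible and would not silently produce false positives.

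**Step 3: a smoker and a non-smoker share one identifier.** This could happen if men were numbered from 1 within each group and that number were used as the subject. Let k = 2T be the values per man. Men are in truth independent, so for one linked pair, with unit variance per observation:

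- True variance of the group difference = 2[1 + (k − 1)ρ] / k.
- Compound symmetry over 2k values averages the true correlations to ρ(k − 1)/(2k − 1), so the model variance = 2[1 − ρ(k − 1)/(2k − 1)] / k.
- True SE / model SE = √{[1 + (k − 1)ρ] / [1 − ρ(k − 1)/(2k − 1)]}.

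At T = 7 (k = 14) and ρ = 0.7: 1 + 13 × 0.7 = 10.1; 1 − 0.7 × 13/27 = 0.663; √(10.1 / 0.663) = 3.90. By normal approximation, type I error is 2[1 − Φ(1.96 / 3.90)], or about 61.5%. Simulation for T = 7:

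| ρ | SE ratio | Type I error, group |
|---|---|---|
| 0.2 | 2.00 | 32.6% |
| 0.5 | 3.14 | 53.3% |
| 0.7 | 3.90 | 61.4% |
| 0.8 | 4.31 | 65.5% |

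Over all settings the range is 26.7% (T = 5, ρ = 0.2) to 69.3% (T = 9, ρ = 0.8). At ρ = 0 it is 4.8% to 4.9%, as it should be. The condition and group-by-condition tests become conservative under the same linking (0.2% to 3.9%), so they add no false positives.

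**Step 4: direct fits.** REML on 150 data sets (T = 7, ρ = 0.7) rejected in 63% with linked men and 7% with unique identifiers. The Monte Carlo standard error around 5% is √(0.05 × 0.95 / 150) = 1.8 percentage points, so 7% is compatible with 5%.

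**Step 5: what separates the two results.** Both Step 2 and Step 3 have group in the repeated list. They differ only in the identifier, which the sentence does not mention.

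**The case for a change.** The strongest case for a change is that a SAP should fix the model before the data are seen, and this sentence is all the SAP says about the time-course model. One of its three named factors is misdescribed, and nothing else in the SAP supplies a subject term to correct it. If group is to vary within a subject at all, a smoker and a non-smoker must share that subject, and the smoking contrast is then badly anticonservative. The correction would be a single sentence and would need no new data.

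Much of this stands. The wording is loose, the arithmetic for linked men is right, and a correction would be cheap. What does not stand is the step from the wording to the harm. Group can be entered in the repeated list while each man keeps his own identifier; he then simply leaves the other group's cells empty. Sharing an identifier requires a numbering scheme or a pairing that the SAP does not contain. An analyst who linked unrelated men in that way would be mishandling the data whether or not group appeared in this sentence.

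**Conclusion.** This is a clerical slip with no expected effect on the results. The fasting and AUC models, in the same paragraph, and the comparison of physical characteristics all treat smoking as an ordinary fixed factor. The natural reading is therefore a repeated-measures mixed model containing condition, group and time, with condition and time repeating within a man. Under that reading, or with group listed as repeated and unique identifiers, type I error for the smoking effect is about 5%. The 27% to 69% range measures a different mistake that the SAP does not describe, and it rests on assumed values for sample size, time points and correlation.

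Two limits apply. That condition varies within a man is inferred from the word repeated. The error rates were checked for compound symmetry and for separate variances by group, not for covariance structures that depend on the order of the cells. Neither limit changes the conclusion: rewording the sentence would tidy the text but would not alter any result that the plan would otherwise give.

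### Does calling an unsigned effect size of 0.2 the minimum important difference, with no confidence interval and no stated link to P < 0.05, require a change to the SAP?

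*SAP*

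**What the plan says.** The effect-size paragraph closes the SAP. "Absolute standardised effect sizes will be calculated by dividing the difference between the mean values" by the pooled standard deviation is the definition, and it serves both the exercise-control and the smoker-non-smoker contrast. The benchmarks follow: "In the absence of a clinical anchor, an effect size of 0.2 will be considered the minimum important difference, 0.5 moderate and 0.8 large". The paragraph ends with the test criterion: "Statistical significance will be accepted as" P < 0.05. No sentence joins the two.

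Confidence intervals appear only in the first paragraph, for log-transformed variables, where "analysis will be based on ratios of geometric means and 95% confidence intervals for ratios". Variables that need no transformation are summarised by mean and SD. The third paragraph specifies linear mixed models for the main outcomes, "with condition (exercise versus control) and group (smokers versus non-smokers) included as fixed factors".

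**The concern.** The words minimum important difference claim more than the label small: they suggest that a d of 0.2 matters. Yet d is planned as a point estimate without sign or interval. Skewed variables get an interval for the effect; normally distributed variables get none in the text. The SAP is also silent on what is reported when d is 0.2 or more and P is not below 0.05, or the reverse.

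If d of 0.2 were read by itself as evidence of an important effect, chance differences would often be called important in small groups, above all between smokers and non-smokers. The same contrasts are applied to many outcomes (diet, activity, HOMA-IR, fasting and AUC plasma constituents, blood pressure), so the question would recur throughout the results.

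**Working it through.** The SAP states no sample size, SD or within-person correlation, so it has no figure to reproduce. Its inputs are the 0.2 benchmark, division by the pooled SD and the 0.05 level (taken as two-sided). Group sizes and correlations below are assumptions.

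**Smokers versus non-smokers, n per group, one value per man, no true difference.** The standard error of d is s = sqrt(2/n), with 2n - 2 degrees of freedom. The chance that |d| exceeds 0.2 is 2 x P(t > 0.2/s). The smallest significant |d| is t(0.975) x s. At n = 12: s = sqrt(2/12) = 0.408 and 0.2/0.408 = 0.49, which on 22 df gives 0.629; the smallest significant |d| is 2.074 x 0.408 = 0.847. At these sizes every significant result also exceeds 0.2, so the share with |d| of at least 0.2 but P not below 0.05 is the first probability minus 0.05.

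| n per group | s | P(\|d\| > 0.2) | smallest significant \|d\| | \|d\| at least 0.2, P not below 0.05 |
|---|---|---|---|---|
| 8 | 0.500 | 0.695 | 1.072 | 0.645 |
| 12 | 0.408 | 0.629 | 0.847 | 0.579 |
| 30 | 0.258 | 0.442 | 0.517 | 0.392 |
| 50 | 0.200 | 0.320 | 0.397 | 0.270 |

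If the smoking contrast averages two conditions per man while d keeps the single-condition SD, s = sqrt((1 + r)/n). With r = 0.5 the 63% at n = 12 becomes 58%, and the 32% at n = 50 becomes 25%.

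**Exercise versus control, if within person, N = 20 men.** Here s = sqrt(2(1 - r)/N), with 19 df.

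| r | s | P(\|d\| > 0.2) | smallest significant \|d\| |
|---|---|---|---|
| 0.5 | 0.224 | 0.382 | 0.468 |
| 0.7 | 0.173 | 0.263 | 0.363 |
| 0.9 | 0.100 | 0.060 | 0.209 |
| 0.95 | 0.071 | 0.011 | 0.148 |

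At r = 0.9 the benchmark and the significance threshold nearly coincide.

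**What the figures measure.** The third column in each table is the false-positive rate of a rule that declares an effect whenever |d| exceeds 0.2. The SAP states no such rule. Its stated criterion is P < 0.05, which keeps the rate at 5% per test whatever d is. The combination in the last column of the first table has a natural reading under the SAP: a difference of at least benchmark size that is not statistically significant.

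**Whether precision is lost to the reader.** For a simple two-group comparison, means, SDs and n give an interval directly. At n = 12 and d = 0.2 it is 0.2 plus or minus 2.074 x 0.408, or -0.65 to 1.05 in SD units (-0.60 to 1.00 by noncentral t). A within-person interval cannot be rebuilt from means and SDs alone, but the planned mixed model produces it. Direction is visible from the two means, so the missing sign hides little.

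**Whether a stricter rule would gain anything.** One could require the whole 95% interval to lie beyond 0.2 before calling a difference important. By noncentral t, the observed smoking |d| would then have to reach about 1.31, 1.07, 0.73 and 0.60 at 8, 12, 30 and 50 per group. Showing a difference smaller than 0.2 needs a half-width of at most 0.2, first met at 194 per group: 1.966 x sqrt(2/194) = 0.1996. At the small sizes assumed here, most smoking contrasts would simply be called inconclusive.

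**The case for a change.** The strongest case for a change is that interpreting effects is a SAP's own job and cannot be left to the protocol. The document names an importance threshold, omits its uncertainty and treats skewed and normal variables unequally, so interpretation could be settled after the results are seen. A few words would cure it, using models already planned.

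The textual part stands: no interval is written down for d or for normally distributed differences, and nothing links d to P. What does not stand is the step from silence to a defect. The mean-and-SD sentence describes how data are summarised, not how model contrasts are reported. The sentence on ratios is needed because back-transformation changes what is estimated, so the contrast between the two does not show that intervals are withheld for normal variables. The benchmark applies only where no clinical anchor exists, and the SAP nowhere says that reaching it establishes an effect. The ease of the cure also cuts the other way: an analyst who fits these models can report the difference and its interval without any further instruction.

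**Conclusion.** No change follows. The SAP omits a reporting detail; it contains no error or contradiction on this point, and carried out as written it gives tests at the stated 5% level. The 32% to 70% figures for the smoking contrast are correct on the assumed group sizes, but they would be error rates only if |d| above 0.2 were itself the decision rule. For exercise versus control the corresponding range is 1% to 38% (20 men, r from 0.95 down to 0.5), and the issue nearly disappears at high correlation.

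A sensible analyst will report signed differences with 95% confidence intervals from the mixed models and treat 0.2, 0.5 and 0.8 as descriptions of size. A formal rule placing the interval against 0.2 SD would be a debatable addition: it would need a choice of SD (by group, condition or model) and would leave most small-sample smoking contrasts undecided. This conclusion rests on reading P < 0.05 as the sole inferential criterion, which is what the text states.
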